	
gastrointestinal or significant urinary bleed within the past six months.
 
18. Subject has had a cerebrovascular accident or transient ischemic neurological attack (TIA) within the past six months, or any prior intracranial bleed, or any permanent neurologic defect, or any known intracranial pathology (e.g. aneurysm, arteriovenous malformation, etc.).
 
19. Subject has extensive peripheral vascular disease that precludes safe 6 French sheath insertion. Note: femoral arterial disease does not exclude the patient if radial access may be used.
 
20. Subject has a life expectancy <5 years for any non-cardiac or cardiac cause.
 
21. Subject is in the opinion of the Investigator or designee, unable to comply with the requirements of the study protocol or is unsuitable for the study for any reason. This includes completion of Patient Reported Outcome instruments.
 
22. Subject is currently participating in another clinical trial that has not yet completed its primary endpoint.
 
23. Subject is part of a vulnerable population who, in the judgment of the investigator, is unable to give Informed Consent for reasons of incapacity, immaturity, adverse personal circumstances or lack of autonomy. This may include: Individuals with a mental disability, persons in nursing homes, children, impoverished persons, persons in emergency situations, homeless persons, nomads, refugees, and those incapable of giving informed consent. Vulnerable populations also may include members of a group with a hierarchical structure such as university students, subordinate hospital and laboratory personnel, employees of the Sponsor, members of the armed forces, and persons kept in detention.

--	---

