Patient Reported Outcome (PRO) Informational Endpoints	
Patient-reported outcomes (PRO) are informational endpoints to assess Health-Related Quality of Life. PRO assessments will be conducted at baseline, 1 and 6 months, and at 1, 3 and 5 years. The following questionnaires will be used in this study:
 

• Seattle Angina Questionnaire-7 (SAQ-7) to assess disease-specific Quality of Life

• EuroQoL 5D (EQ-5D) survey to assess overall health status

 
(Note: PRO endpoints will be evaluated in the ~2600 subjects of ABSORB IV)
 
The PROs will be analyzed to evaluate the relationship between quality of life and cardiovascular events that occurred post-PCI and to substantiate the clinical impact of the angina events identified in the trial.

Health Economics Informational Endpoints	The primary analysis is to compare the resource utilization and costs between the two treatment groups at 1, 2 and 3 years. If the rates of angina, hospitalizations or revascularizations are different between the two arms, a cost effectiveness analysis will be performed evaluating the cost of angina, hospitalizations or revascularizations avoided.
Subject Enrollment, Randomization and Registration	

• Subjects are considered enrolled in ABSORB IV after signing the Informed Consent.

• Subjects are considered randomized in ABSORB IV after the interactive voice response system (IVRS) has been called and a device (Absorb BVS or XIENCE) has been assigned.

• Subjects are considered registered in the ABSORB IV upon randomization.

• Enrolled subjects not randomized in the trial will be considered screen failures and will not be followed.

Clinical Follow-Up	All registered subjects in ABSORB IV will receive the following clinical follow-up: 

○ <math>30 \pm 7</math> days follow-up telephone contact/office visit

○ <math>90 \pm 14</math> days follow-up telephone contact/office visit

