## 5.4 Informational Endpoints

### 5.4.1 Patient Reported Outcomes

Patient-reported outcomes are informational endpoints to assess Health-Related Quality of Life at baseline, 1, 6, 12 months and will be assessed at 3 and 5 years throughout the remaining duration of the trial. These PRO endpoints will be evaluated in the ~2600 subjects of ABSORB IV. The following questionnaires will be used in this study:

- Seattle Angina Questionnaire-7 (SAQ-7) to assess disease-specific Quality of Life
- EuroQoL 5D (EQ-5D) survey to assess overall health status

The PROs will be analyzed to evaluate the relationship between quality of life and cardiovascular events that occurs post-PCI and to substantiate the clinical impact of the angina events identified in the trial.

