**Confidential and Proprietary**

**Do not distribute or reproduce without the prior written permission of Abbott Vascular Inc.  
ABSORB III Randomized Control Trial Version 17.0 August 16, 2018.**

$H_A: \text{ANGINA}_{\text{Absorb}} - \text{ANGINA}_{\text{XIENCE}} < \Delta_{\text{ANGINA}}$ .

$\text{ANGINA}_{\text{Absorb}}$  and  $\text{ANGINA}_{\text{XIENCE}}$  are the percentage of patients with angina within 1 year in the Absorb BVS and XIENCE arms, respectively.  $\Delta_{\text{ANGINA}}$  is the non-inferiority margin for this secondary endpoint.

The power calculation for the Angina Secondary Endpoint within 1 year is based on the following assumptions:

- The true percentage of patients with angina within 1 year is assumed to be 22.6% for both the Absorb BVS arm and the XIENCE arm
- One-sided alpha: 2.5%
- Non-inferiority margin ( $\Delta_{\text{ANGINA}}$ ): 7%
- Randomization ratio (ABSORB IV): 1 (Absorb BVS arm) : 1 (XIENCE arm)
- 5% loss to follow-up at 1 year

With the effective sample size 2470 (Absorb: 1235, XIENCE: 1235) at 1 year, the study has approximately 99% power to demonstrate non-inferiority of Absorb BVS to XIENCE using Farrington and Manning test.

If the non-inferiority of Absorb BVS to XIENCE is demonstrated and the percentage is lower in Absorb BVS compared to XIENCE, a superiority test will be performed at the two sided alpha 0.05 level.

The null ( $H_0$ ) and alternative ( $H_A$ ) hypotheses are:

$H_0: \text{ANGINA}_{\text{Absorb}} - \text{ANGINA}_{\text{XIENCE}} = 0$

$H_A: \text{ANGINA}_{\text{Absorb}} - \text{ANGINA}_{\text{XIENCE}} \neq 0$

$\text{ANGINA}_{\text{Absorb}}$  and  $\text{ANGINA}_{\text{XIENCE}}$  are the percentage of patients with angina within 1 year in the Absorb BVS and XIENCE arms, respectively.

With the effective sample size 2470 at 1 year, the study has approximately 86% power to demonstrate superiority with a difference of 4.9% between the Absorb BVS arm and the XIENCE arm (e.g. 17.7% in the Absorb BVS arm vs. 22.6% in the XIENCE arm) using Pearson's Chi-square test.

The sample size calculations were performed using NCSS PASS 11 (Hintze, J., 2011, NCSS, LLC. Kaysville, Utah).

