#### ***10.4.5 Informational Endpoint Analyses***

Details on informational endpoint analyses can be found in the SAP.

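### ABSORB IV reports cost-effectiveness only if event rates differ, and uses those same events as the effect measure, so a reported effect is biased away from zero

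*Combined protocol and SAP*

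**What the plan says.** The Health Economics row of the ABSORB IV Protocol Summary contains two rules. The first is unconditional: "The primary analysis is to compare the resource utilization and costs between the two treatment groups at 1, 2 and 3 years". The second is conditional: "If the rates of angina, hospitalizations or revascularizations are different between the two arms, a cost effectiveness analysis will be performed", with the content of that analysis given as "evaluating the cost of angina, hospitalizations or revascularizations avoided". The three outcomes in the condition are the three outcomes in the effect measure.

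No test, significance level, direction or time point is attached to the word *different*. Nothing says whether the analysis covers all three outcomes or only some of them.

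The Introduction (Section 1) and Section 5.4.2 of the ABSORB IV part speak of comparing costs and collecting billing data, the latter at United States sites only. Neither provides an unconditional cost-effectiveness analysis. Section 10.4.5 says only: "Details on informational endpoint analyses can be found in the SAP". The combined document contains no ABSORB IV SAP text.

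Section 5.4.1 lists the "EuroQoL 5D (EQ-5D) survey to assess overall health status" for all of the roughly 2600 subjects, but no analysis of cost against utility is stated.

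**The concern.** A cost-effectiveness analysis estimates two differences, in cost and in effect, together with their uncertainty. It does not need a demonstrated effect first. If the ratio is computed only after the data show a difference, trials in which chance enlarged the effect are kept and trials in which chance shrank it are dropped. The effect that reaches the report is then too large on average, most of all when the true difference is small. A reader of the report sees a cost per event avoided and cannot tell that its denominator passed through a filter.

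What is at stake is the credibility of one informational result. The trial's conclusion on target lesion failure or angina is not at risk.

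**Working it through.** **Inputs.** Of the three trigger outcomes, only angina has ABSORB IV design figures. Section 10.3.2 (Powered Secondary Endpoint 2) gives "17.7% in the Absorb BVS arm vs. 22.6% in the XIENCE arm", a 4.9-point difference; 1235 subjects per arm (2600 × 0.95 = 2470); and "a superiority test will be performed at the two sided alpha 0.05 level".

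**Step 1: reproduce the plan's own figure.** The plan states: "With the effective sample size 2470 at 1 year, the study has approximately 86% power". The standard error (SE) is √[(0.177 × 0.823 + 0.226 × 0.774)/1235] = 0.0161, so power is Φ(0.049/0.0161 − 1.96) ≈ 86%. The standard two-proportion formula gives 85.9%. The stated figure reproduces.

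**Step 2: expected angina estimate, given that the analysis runs.** Let d be the true difference (XIENCE minus Absorb, XIENCE at 22.6%) and c the trigger threshold in standard errors. For a normally distributed estimate,

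E(estimate | triggered) = d + SE × φ(c − d/SE) / [1 − Φ(c − d/SE)].

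Two readings of *different* bracket the range: significant at two-sided 0.05 in Absorb's favour (c = 1.96), and any numerically lower rate (c = 0).

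| True d (points) | SE | Chance of trigger, c = 1.96 | Expected estimate | Ratio to truth | Chance of trigger, c = 0 | Expected estimate | Ratio to truth |
|---|---|---|---|---|---|---|---|
| 0 | 1.68 | 2.5% | 3.9 | – | 50% | 1.3 | – |
| 1 | 1.67 | 8.7% | 4.0 | 4.0 | 72.5% | 1.8 | 1.77 |
| 2 | 1.66 | 22.6% | 4.2 | 2.1 | 88.6% | 2.4 | 1.18 |
| 3 | 1.64 | 44.8% | 4.5 | 1.48 | 96.6% | 3.1 | 1.04 |
| 4.9 | 1.61 | 86.0% | 5.3 | 1.08 | 99.9% | 4.9 | 1.00 |

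Using one standard error throughout, √(2 × 0.226 × 0.774/1235) = 1.68 points, moves the c = 1.96 results to 4.3 at a true 2 points and 5.4 at 4.9 (5.4/4.9 = 1.10). Under that reading an observed difference below about 1.96 × 1.68 = 3.3 points cannot trigger the analysis. If the analysis ran regardless, every ratio would be 1.

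**Step 3: chance of a trigger when nothing differs.** With three independent outcomes at two-sided 0.05, the chance that at least one differs in either direction is 1 − 0.95³ = 14.3%. Simulation with assumed correlations of 0.3, 0.5 and 0.8 gives 13.6%, 12.5% and 9.9%. Counting only differences that favour Absorb, the chance is 1 − 0.975³ = 7.3% if independent and 4.9% at a correlation of 0.8. The documents give no ABSORB IV rates for hospitalization or revascularization and no correlations, so these are assumptions.

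**The case against.** The strongest reply is that a cost per event avoided is unstable or undefined when the event difference is near zero, so reporting it only when there is a difference is ordinary prudence. The instability is real. The usual answer is to report the two differences and their joint uncertainty, which stay well defined when the ratio does not. Withholding the ratio does not remove the selection from the trials that do report it.

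A second reply is that *different* is undefined here and the SAP may settle it. That stands as far as it goes: the size of the bias cannot be fixed from the protocol. But both readings in the table leave some bias for small true effects. A definition in the SAP would narrow the range, but the condition itself would remain.

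Some stronger readings are tempting and are not supported:

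- *That the cost question goes unanswered when no rate differs.* Costs and resource use are compared at 1, 2 and 3 years in any event. Only the cost-effectiveness step is conditional.
- *That the plan uses whichever outcome differs.* The text repeats the same list in the condition and in the analysis, and gives no rule for choosing among its items.
- *That 14% of null trials would show a spurious gain of about 3.9 points for Absorb.* The 14% counts either direction; the 3.9 is the mean in one direction. With a trigger in either direction and no true difference, the signed mean is zero and only its size is inflated.
- *That cost per angina case avoided would be understated twofold.* The documents contain no cost figures. Fewer events would also change costs, and if the better arm is also the cheaper one the statement has no meaning.

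**Conclusion.** The point holds, as a minor one. As worded in the Protocol Summary, the analysis is conditional on the data that also form its effect estimate, and nothing elsewhere in the protocol provides an unconditional version.

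At the planned angina effect the exaggeration is small: 8 to 10% under a significance trigger and none under the loosest reading. It matters if the true effect is modest: at 2 points it is about twofold under the first reading and about 1.2-fold under the second. These figures assume a normal approximation, a 22.6% XIENCE rate, and that angina itself is the outcome that triggers the analysis. If another outcome triggers it, the angina estimate is affected only through its correlation with that outcome.

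The primary endpoint, both powered secondary endpoints, and the comparison of costs and resource use are unaffected. A reader might infer that the plan was built to favour Absorb. The text gives the trigger no direction, and the documents do not support that inference.

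**What to change.** Delete the condition. State that the cost-effectiveness analysis will be done whatever the event results, for angina, hospitalizations and revascularizations alike, at time points named in advance. Report the cost difference and the effect difference for each outcome with their joint uncertainty, for example by bootstrapping subjects, and give the ratio as a derived quantity. State also how the US-only billing data will be handled: restrict the analysis to those sites, or apply a stated costing rule to the others.

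If utility from EQ-5D is added, use the scheduled visits (baseline, 30 and 180 days, 1, 3 and 5 years). There is no 2-year visit for this questionnaire, so a 2-year result needs an interpolation rule stated in advance.

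The cost is a few sentences in the protocol and SAP and some extra analysis, with no new data collection. The drawback is that ratios will be imprecise when event differences are near zero, which the joint uncertainty will show.

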#### **Angiographic Exclusion Criteria**

All exclusion criteria apply to the target lesion(s) or target vessel(s).

 This includes clinical trials of medications and invasive procedures. Questionnaire-based studies, or other studies that are non-invasive and do not require medication are allowed. A subject who is taking part in the long-term follow-up phase of a trial, who has completed all medications and invasive procedures per protocol requirements, may continue to participate in that trial.

	

1. Unsuccessful pre-dilatation, defined as the presence of one or more of the following (note: successful pre-dilatation of at least one target lesion is required prior to randomization):

a. Residual %DS after pre-dilatation is <math>\geq 40\%</math> (per visual estimation). Note: achieving a %DS <math>\leq 20\%</math> prior to randomization is strongly recommended.

b. TIMI flow grade <math><3</math> (per visual estimation).

c. Any angiographic complication (e.g. distal embolization, side branch closure).

d. Any dissection NHLBI grade D-F.

e. Any chest pain lasting <math>> 5</math> minutes.

f. Any ST-segment depression or elevation lasting <math>> 5</math> minutes.

2. Lesion is located in left main or there is a <math>\geq 30\%</math> diameter stenosis in the left main (unless the left main lesion is a protected left main (i.e. a patent bypass graft to the LAD and/or LCX arteries is present), and there is no intention to treat the protected left main lesion).

3. Aorto-ostial RCA lesion (within 3 mm of the ostium).

4. Lesion located within 3 mm of the origin of the LAD or LCX.

5. Lesion involving a bifurcation with a:

a. side branch <math>\geq 2</math> mm in diameter, or

b. side branch with either an ostial or non-ostial lesion with diameter stenosis <math>> 50\%</math>, or

c. side branch requiring dilatation

6. Anatomy proximal to or within the lesion that may impair delivery of the Absorb BVS or XIENCE stent:

a. Extreme angulation (<math>\geq 90^\circ</math>) proximal to or within the target lesion.

b. Excessive tortuosity (<math>\geq</math> two <math>45^\circ</math> angles) proximal to or within the target lesion.

c. Moderate or heavy calcification proximal to or within the target lesion. If IVUS used, subject must be excluded

--	---

	
if calcium arc in the vessel prior to the lesion or within the lesion is <math>\geq 180^\circ</math>.
 
7. Lesion or vessel involves a myocardial bridge.
 
8. Vessel has been previously treated with a stent and the target lesion is within 5 mm proximal or distal to a previously stented lesion.
 
9. Target lesion located within an arterial or saphenous vein graft or distal to any arterial or saphenous vein graft.

Lesion Selection	
Prior to treatment with the assigned device (Absorb BVS or XIENCE), vessel sizing by visual estimation must be conducted to appropriately match the device to the size of the vessel. Quantitative methods such as on-line QCA, IVUS or OCT may be used if the site is experienced with these techniques. Specifically, use of pre-PCI and post-PCI IVUS or OCT is strongly recommended to optimize device sizing and results. Details on the vessel sizing methods can be found in the Imaging Guidance Document. Table 1.0 provides the device sizes, the reference vessel diameter (RVD) and lesion length for ABSORB IV.

**Table 1.0** Absorb BVS and XIENCE Sizes in ABSORB IV

Device	Lesion and Device Sizes	
	RVD 	Lesion Length 
Absorb BVS (Target lesion)	RVD $\geq 2.50$ mm - $\leq 3.75$ mm Scaffold diameter: 2.5, 3.0 and 3.5 mm	Lesion length $\leq 24$ mm Scaffold Length  : 8, 12, 18 and 28 mm 
XIENCE  (Target lesion)	RVD $\geq 2.50$ mm - $\leq 3.75$ mm Stent diameter: 2.5, 2.75, 3.0, 3.25 3.5, 4.0 mm	Lesion length $\leq 24$ mm Stent Length: 8, 12, 15, 18, 23 and 28 mm 

 Reference vessel diameter (RVD) and lesion length are based on visual estimation.

 Both the 8 mm and 12 mm lengths will be available for the 2.5/3.0 diameter Absorb BVS. Only the 12 mm length will be available for the 3.5 mm diameter. The commercially approved CE marked 23mm Absorb BVS device will not be used in this study.

 For target lesion, planned overlapping is not allowed (i.e. the lesion must be eligible for treatment with a single stent). However, bailout overlapping is allowed if required.

 XIENCE V, XIENCE Prime, XIENCE Xpedition, XIENCE Alpine, XIENCE Pro, and XIENCE ProX will be used in this study.

It is highly recommended that a minimum of 2 mm (by visual estimation) of normal or nearly normal reference vessel at both proximal and distal edge be covered by the device.

Treatment Strategy	

• Treatment of up to three de novo lesions in a maximum of two epicardial vessels, with a maximum of two lesions per epicardial vessel.

• If only a single lesion is to be treated, it must be a target lesion, treated with the assigned device (Absorb or XIENCE).

• Non-target lesion treatment can occur only in a non-target vessel.

• The treatment possibilities are:

○ Single target lesions

○ Two or three target lesions

○ One target lesion and one non-target lesion

○ Two target lesions and one non-target lesion

• All target lesions must meet angiographic inclusion/exclusion criteria.

• The non-target lesion must be treated first with a XIENCE, before randomization, per the instructions for use (IFU). A non-target lesion cannot be considered for a staged procedure. The patient may then only be randomized if treatment of the non-target lesion was successful and uncomplicated, defined as:

○ final diameter stenosis <math>\leq</math> 10% with final TIMI-3 flow,

○ with no residual dissection NHLBI grade <math>\geq</math> type B, and

○ no transient or sustained angiographic complications (e.g., distal embolization, side branch closure),

○ no chest pain lasting <math>></math> 5 minutes, and

○ no ST segment elevation or depression lasting <math>></math> 5 minutes.

• If there are two target lesions within the same epicardial vessel, the two target lesions must be at least 15 mm apart; otherwise this should be considered a single target lesion for lesion (and stent) length determination and must be treated with a single study device.

	Access Site and Guide Catheter Size: 

• Either femoral or radial access may be used.

 The definition of epicardial vessels means the LAD, LCX and RCA and their branches.

- A minimum 6F guide catheter or greater must be used during the index procedure per requirements for Absorb BVS implantation (refer to IFU).
  - Minimum guiding catheter compatibility (inner diameter) for Absorb BVS is 0.070"/1.8 mm (6F).
  - Devices (i.e., guide sheaths such as the GuideLiner) that decrease the inner diameter of the guide catheter outside of the Absorb BVS minimum guide catheter compatibility must not be used with the Absorb BVS System. Do not insert a 5-in-6, or a 6-in-7 guide sheath into a 6F or 7F guiding catheter, respectively, as doing so will result in an inner diameter that is too small for use with the Absorb BVS.
  - If a guide sheath is necessary, the inner diameter must meet or exceed the above minimum guiding catheter requirements for Absorb BVS (i.e., only the 7-in-8 GuideLiner provides an adequate inner diameter (0.071" ID), 8F guiding catheter would be required).
  - For XIENCE, please follow IFU for guiding catheter size.

**Baseline angiogram and identification of the potential target lesion:**

- Assessment of the potential target lesion(s) to be treated must be done to ensure angiographic criteria are met; this must occur prior to pre-dilatation and vessel sizing. Refer to the Imaging Guidance Document.
- To exclude enrollment of excessively small vessels, if the operator believes that based on visual angiographic assessments, the distal reference vessel diameter is  $\leq 2.75$  mm such that the plan is to implant a 2.5 mm device (stent or scaffold) in a target lesion, it is strongly recommended that either on-line QCA or intravascular imaging (ultrasound or optical coherence tomography) is used and demonstrates that the measured distal RVD for this target lesion is  $\geq 2.50$  mm (by at least one of these imaging modalities). This measurement may be performed before or after pre-dilatation, but before randomization. If the distal RVD measures  $<2.5$  mm, that lesion IS NOT ELIGIBLE for randomization. Such a lesion may be treated as a non-target lesion.

**Pre-dilatation of potential target lesion(s)**

	

• Pre-dilatation of at least one of the planned target lesions(s) must be performed and be successful before calling IVRS. However, each target lesion must be pre-dilated before device implantation in that lesion.

• Pre-dilatation must be performed with an angioplasty balloon; cutting or scoring balloons may be used per physician discretion.

• The pre-dilatation balloon should be sized 1:1 to the visually estimated RVD and should be no more than 0.25 mm smaller than RVD. If the pre-dilatation balloon is sized 1:1 a non-compliant balloon is strongly recommended.

 
The pre-dilatation balloon must be equal in length or shorter than the planned scaffold/stent length.
 
Important: Full balloon expansion with the pre-dilatation balloon must be achieved before the patient is randomized into the study. If there is any question that the target lesion was not fully dilated or that any significant resistance to expansion from the lesion remains, the lesion should be re-dilated with a non-compliant balloon (sized 1:1 to the RVD) at higher pressure. Absorb BVS or XIENCE must not be implanted in a lesion in which full balloon expansion has not been achieved.
 

• The potential target lesion(s) must continue to meet angiographic criteria following adequate pre-dilatation, to be regarded as “successful pre-dilatation”.

○ RVD remains <math>\geq 2.50</math> mm - <math>\leq 3.75</math> mm, and length of the lesion that will be covered by the device (including any edge dissections) is still <math>\leq 24</math> mm.

○ Residual %DS is a maximum of <math>< 40\%</math> (per visual estimation); <math>\leq 20\%</math> is strongly recommended.

○ TIMI Grade 3 flow (per visual estimation).

○ No angiographic complications (e.g. distal embolization, side branch closure).

○ No dissections NHLBI grade D-F.

○ No chest pain lasting <math>> 5</math> minutes.

○ No ST-segment depression or elevation lasting <math>> 5</math> minutes.

--	---

- For two or three potential target lesions, the lesion with the highest possibility of failing eligibility criteria after pre-dilatation (per investigator's assessment) should be identified as the 1st target lesion and pre-dilated first before randomization.
  - If the 1st target lesion was successfully pre-dilated and eligibility criteria are still met, the operator may at this point choose to randomize the patient, or pre-dilate other lesions. If other lesions are pre-dilated, all such pre-dilatations must be considered successful according to the above criteria prior to randomization. If there are two target lesions in a single epicardial coronary artery, it is strongly recommended that both be successful pre-dilated before the patient is randomized. The IVRS is called to randomize the subject. All target lesions must be treated with the assigned device.
  - If the 1st target lesion was successfully pre-dilated but did not meet vessel sizing criteria, treat as a non-target lesion. Once the first lesion is successfully treated as a non-target lesion, the second lesion or third lesion must meet successful predilatation and vessel sizing criteria. Afterwards IVRS must be called and the target lesion(s) will be treated per assignment.
  - If pre-dilatation of the 1st target lesion fails (or if pre-dilatation of any lesion fails if multiple lesions are pre-dilated prior to randomization), the patient may not be randomized, and the interactive voice response system (IVRS) must not be called. The lesion will be treated with XIENCE or standard of care.
  - If the 1st target lesion was successfully pre-dilated but no longer met eligibility criteria (or if any lesion after pre-dilatation no longer met eligibility criteria if multiple lesions are pre-dilated prior to randomization), the patient may not be randomized, and the interactive voice response system (IVRS) must not be called.
  - If after successful pre-dilatation, randomization and treatment of the 1st target lesion with the assigned device, and pre-dilatation of the 2nd or 3rd target lesion failed, the patient is to be treated with XIENCE. For any lesion in which pre-dilatation did not meet the success definition, the default device is XIENCE.
- Each target vessel and lesion should also be such that the operator believes either the Absorb BVS or XIENCE devices could be delivered to and cross the target lesion after pre-

	
dilatation (e.g. absence of excessive vessel or lesion tortuosity or calcification).
 <h3>Vessel Sizing</h3> 

Following the use of nitroglycerine (at least 100 µg intracoronary nitroglycerine, >150 µg preferred) and successful pre-dilatation of the potential target lesion(s), vessel sizing must be conducted by visual estimation. If nitroglycerine is not available, intravenous nitroprusside or intravenous calcium channel blocker may be used per physician discretion.

Quantitative methods such as on-line QCA, IVUS or OCT may be used if the site is experienced with these techniques, taking into account that QCA tends to under-estimate RVD compared to visual estimation and OCT, whereas IVUS tends to over-estimate lumen RVD compared to visual estimation and OCT. Specifically, use of pre-PCI and post-PCI IVUS or OCT is strongly recommended to optimize device sizing and results. Follow core laboratory guidelines for the use of each modality.

Prior to randomization, IVUS or OCT can be used to evaluate the vessel if there is question regarding the eligibility of the vessel either before or after pre-dilatation. Specifically, to exclude enrollment of excessively small vessels, if the operator believes that based on visual angiographic assessments, the distal reference vessel diameter is <math>\leq 2.75</math> mm such that the plan is to implant a 2.5 mm device (stent or scaffold) in a target lesion, it is strongly recommended that either on-line QCA or intravascular imaging (ultrasound or optical coherence tomography) is used and demonstrates that the measured distal RVD for this target lesion is <math>\geq 2.50</math> mm (by at least one of these imaging modalities). This measurement may be performed before or after pre-dilatation, but before randomization. If the distal RVD measures <math><2.5</math> mm, that lesion IS NOT ELIGIBLE for randomization. Such a lesion may be treated as a non-target lesion. A subject must not be randomized in ABSORB IV if:

Vessel size or lesion length before or after pre-dilatation does not satisfy eligibility criteria.

Moderate or heavy calcification, tortuosity or other conditions are present proximal or within the target

--	---

 If the patient's blood pressure is so low that  $\geq 100$  µg of nitroglycerine cannot be administered, the patient should not be randomized. It is suggested that  $\geq 200$  µg of nitroglycerine be administered if the systolic blood pressure is  $>140$  mmHg. Timing of nitroglycerine administration and pre-dilatation is per physician discretion, but must be before randomization and assessment of scaffold or stent size.

	
segment, reducing the likelihood that the Absorb BVS or XIENCE can be either delivered to or expanded at the lesion.
 

○ Complications and/or adverse events were identified during IVUS or OCT usage (e.g. vessel dissection NHLBI grade D-F).

● Table 2.0 provides the guidance of vessel and device sizing during the procedure, which are detailed as the following:

○ First, assess RVD based on visual estimation

○ Then, select a pre-dilatation balloon sized 1:1 to RVD or 0.25 mm smaller than RVD. For example, for RVD of 2.5 mm, a pre-dilatation balloon of 2.25 or 2.5 mm should be used.

○ Use the size of the inflated pre-dilatation balloon, as well as the results after pre-dilatation, to reassess the RVD for appropriate vessel sizing for the scaffold or stent. If the reassessed RVD after pre-dilatation exceeds the specified range for a specific BVS size, the next available size Absorb BVS can be used. For example, if the RVD is reassessed as 2.8 mm after pre-dilatation of a vessel that was believed to be 2.5 mm before pre-dilatation, then implant a 3.0 mm BVS.

○ Post-dilatation of the scaffold is strongly recommended for all Absorb treated lesions, especially for any implanted 2.5 mm ABSORB scaffolds.

○ For patients randomized to XIENCE, the decision to post-dilate should be made according to standard practice.

○ Post-dilatation must always be performed with a non-compliant balloon, sized 1:1 to the vessel, using at least 16 atm of pressure.. Always make sure the non-compliant post-dilatation balloon has a length short enough so it is inflated within the scaffold margins to avoid edge dissection. The delivery balloon should not be used for post-dilatation.

Table 2.0	Vessel and Device Sizing

 Examples of complications associated with IVUS or OCT: side-branch occlusion, persistent S-T abnormalities, prolonged chest pain, flow limiting dissections etc.

Closest RVD by Visual Estimation	Pre-dilatation Balloon Diameter	Reassessed Closest RVD after Pre-dilatation	Absorb BVS Diameter
2.5 mm	2.25 or 2.5 mm	2.5 mm	2.5 mm
2.75 mm	2.5 – 2.75 mm	2.75 mm	3.0 mm
3.0 mm	2.75 – 3.0 mm	3.0 mm	3.0 mm
3.25 mm	3.0 – 3.25 mm	3.25 mm	3.5 mm
3.5 mm	3.25 – 3.5 mm	3.5 mm	3.5 mm
3.75 mm	3.5 – 3.75 mm	3.75 mm	3.5 mm

